9.4.8 Treatment Compliance

Records of treatment compliance for each subject will be kept during the Treatment Phase of the study. CRAs will review treatment compliance during site visits and at the completion of the study.

9.4.9 Drug Supplies and Accountability

In compliance with local regulatory requirements, drug supplies will not be sent to the investigator (or if regionally required, the head of the medical institution or the designated pharmacist) until the following documentation has been received by the sponsor:

- A signed and dated confidentiality agreement
- A copy of the final protocol signature page, signed and dated by both the sponsor and investigator
- Written proof of approval of the protocol, the ICFs, and any other information provided to the subjects by the IRB/IEC for the institution where the study is to be conducted
- A copy of the IRB/IEC-approved ICF and any other documentation provided to the subjects to be used in this study

- The IRB/IEC membership list and statutes or Health and Human Services Assurance number
- A copy of the certification and a table of the normal laboratory ranges for the reference laboratory conducting the clinical laboratory tests required by this protocol
- An investigator-signed and dated FDA Form FDA 1572, where applicable
- Financial Disclosure form(s) for the principal investigator and all subinvestigators listed on Form FDA 1572, where applicable
- A signed and dated curriculum vitae of the principal investigator including a copy of the principal investigator's current medical license (required for United States sites) or medical registration number on the curriculum vitae
- A signed and dated Clinical Trial Agreement (CTA)
- A copy of the regulatory authority approval for the country in which the study is being conducted (if required), and the Import License (if required)

The investigator and the study staff (or if regionally required, the head of the medical institution or the designated pharmacist) will be responsible for the accountability of all study drugs (dispensing, inventory, and record keeping) following the sponsor's instructions and adherence to GCP guidelines as well as local or regional requirements.

Under no circumstances will the investigator allow the study drugs to be used other than as directed by this protocol. Study drugs will not be dispensed to any individual who is not enrolled in the study.

The site must maintain an accurate and timely record of the following: receipt of all study drugs, dispensing of study drugs to the subject, collection and reconciliation of unused study drugs that are either returned by the subjects or shipped to site but not dispensed to subjects, and return of reconciled study drugs to the sponsor or (where applicable) destruction of reconciled study drugs at the site. This includes, but may not be limited to: (a) documentation of receipt of study drugs, (b) study drugs dispensing/return reconciliation log, (c) study drugs accountability log, (d) all shipping service receipts, and (e) documentation of returns to the sponsor. All forms will be provided by the sponsor. Any comparable forms that the site wishes to use must be approved by the sponsor.

The study drugs and inventory records must be made available, upon request, for inspection by a designated representative of the sponsor or a representative of a health authority (eg, FDA, Medicines and Healthcare Regulatory Agency). As applicable, all unused study drugs and empty and partially empty containers from used study drugs are to be returned to the investigator (or if regionally required, the head of the medical institution or the designated pharmacist) by the subject and, together with unused study drugs that were shipped to the site but not dispensed to subjects, are to be returned to the sponsor's designated central or local depot(s) during the study or at the conclusion of the study, unless provision is made by the sponsor for destruction of study drugs and containers at the site. Destruction at the site will only occur under circumstances where regulation or supply type prohibits the return of study drugs to the central or local depot(s). Approval for destruction to occur at the site must be provided by the sponsor in advance. Upon completion of drug accountability and

reconciliation procedures by the site's personnel and documentation procedures by the sponsor's personnel, study drugs that are to be returned to the sponsor's designated central or local depot(s) must be boxed, sealed, and shipped back to the central or local depot(s) following all local regulatory requirements. In some regions, study drugs may be removed from the site and hand delivered to the central or local depot by sponsor representatives. Where study drugs are approved for destruction at the site, destruction will occur following the site's standard procedures and certificates of destruction will be provided to the sponsor.

Drug accountability will be reviewed during site visits and at the completion of the study.

9.5 Study Assessments

9.5.1 Assessments

9.5.1.1 Demography

Subject demography information will be collected at the Screening Visit. Demography information includes date of birth (or age), sex, race/ethnicity, native language, handedness, and highest education level.

9.5.1.2 Baseline Assessments

Assessments to be made at Screening and Baseline and throughout the study are described in [Section 9.5.1.3](#), [Section 9.5.1.4](#), and [Section 9.5.1.5](#).

9.5.1.2.1 MEDICAL HISTORY AND PHYSICAL EXAMINATIONS

Medical and surgical history, current medications including AChEI and memantine use, and current medical conditions will be recorded at the Screening Visit. All medical and surgical history within 10 years must be noted in the Medical History and Current Medical Conditions eCRF. Medical history will include history of cognitive impairment due to AD. Subjects will be asked about history of TB, infections due to varicella zoster virus (chickenpox and herpes zoster/shingles) and HSV Types 1 and 2 (orolabial herpes/cold sores and genital herpes, respectively). The medical history of such infections will include onset, duration, relapse frequency, severity, and treatments. Subjects will also be asked about their vaccination history including vaccinations against varicella zoster virus and TB. The 15-item GDS and modified Hachinski ischemic scale will also be assessed at Screening as part of the exclusion criteria.

Physical examinations (complete or routine) will be performed as designated in [Table 6](#). A complete physical examination will include evaluations of the head, eyes, ears, nose, throat, neck, chest (including heart and lungs), abdomen, limbs, and skin, and a neurological examination. A urogenital examination will only be required in the presence of clinical symptoms related to this region. Documentation of the physical examination will be included in the source documentation at the site. Significant findings at the Screening Visit will be recorded on the Medical History and Current Medical Conditions eCRF. Changes

from screening physical examination findings that meet the definition of an AE will be recorded on the Adverse Events eCRF.

9.5.1.2.2 VIRAL TESTING

As specified in [Table 6](#), blood will be collected for screening for Hepatitis B and Hepatitis C for determining eligibility, and at Baseline for viral characterization.

9.5.1.2.3 B12 TESTING

Blood will also be collected for vitamin B12 levels as specified in [Table 6](#).

9.5.1.2.4 TB EXPOSURE TESTING

Blood will also be collected for testing for previous TB exposure, as specified in [Table 6](#).

9.5.1.2.5 URINE DRUG TESTING

Urine will be collected for drug screening as specified in [Table 6](#).

9.5.1.3 Efficacy Assessments

9.5.1.3.1 PSYCHOMETRIC ASSESSMENTS

The timing of psychometric assessments is shown in [Table 6](#) and [Table 7](#). These assessments should be administered in the morning (or, if not possible, consistently at the same time of day) and should be completed before more invasive assessments or procedures (eg, physical examination, ECG, blood draws). The order of assessments is: MMSE, CDR, FAQ, ISLT (immediate recall), CBB, and ISLT (delayed recall) at Screening; and MMSE, CDR, ADAS-cog₁₄, FAQ, ISLT (immediate recall), CBB, and ISLT (delayed recall) at the Baseline Visit.

At visits where the CDR or FAQ are conducted, the investigator will determine whether the caregiver or informant must attend in person or whether telephone contact will be suitable, and will base this determination upon the functional ability of the subject among other factors.

The Derived Alzheimer's Disease Composite Score: The primary efficacy endpoint is the change from baseline in the derived ADCOMS at 18 months of treatment in MCI/Prodromal subjects.

The ADCOMS is derived from the ADAS-cog (4 items), the MMSE (2 items), and the CDR (all 6 items), described below. The ADCOMS is more sensitive to clinical progression compared with currently existing clinical batteries and requires smaller sample sizes for clinical studies in MCI/Prodromal AD or mild AD. It also shows sensitivity to treatment effects with AChEIs. The ADCOMS assesses both cognitive and functional domains and can be offered as a single primary clinical endpoint. The ADCOMS has a range from 0 to 1.97.

CogState Brief Battery: The CBB is a computer-based battery comprising 4 cognitive tests:

1. Detection – a simple reaction time test where the subject presses a key when the card is turned face up from a pack of cards (“Has the card turned over”). Speed of response is the measure.
2. Identification – a simple choice reaction time test where the subject presses 1 of 2 keys when the card just turned face up is either a red card or a black card (“Is the card red”). Speed of response is the measure.
3. One Card Back – a simple working memory test where the subject presses 1 of 2 keys when the card turned face up is either the card seen in the immediately previous trial or not (“Is the previous card the same”). Accuracy of response is the measure.
4. One Card Learning – a visual learning and memory test where the subject presses 1 of 2 keys depending on whether the card just turned face up has been seen before or not in the task (“Have you seen this card before in this task”). Accuracy of response is the measure.

ISLT: The ISLT is a verbal learning and episodic memory test assessing both immediate and delayed recall. Subjects are read a list of 12 items that can be obtained at the local shopping center. Subjects are asked to recall as many of the items as possible and this immediate recall trial is repeated 3 times. After a delay of approximately 15 minutes, in which time the CBB is performed, subjects are again asked to recall as many of the words on the shopping list as they can (ie, a delayed recall trial).

Mini Mental State Examination: A 30-point scale that measures orientation to time and place, registration, immediate and delayed recall, attention, language, and drawing. Scores range from 0 (most impaired) to 30 (no impairment).

Clinical Dementia Rating: The CDR assesses 6 domains of subject function; memory, orientation, judgment and problem solving, community affairs, home and hobbies and personal care. Each of these items has a maximum possible score of 3 points and the total score is a sum of the item scores (sum of boxes) giving a total possible score of 0 to 18 with higher scores indicating more impairment.

Alzheimer's Disease Assessment Scale - cognitive subscale: Discussed in [Section 9.2.4](#).

Functional Assessment Questionnaire: Either a caregiver or informant or the subject provides performance ratings (from 0 to 3) on 10 complex activities of daily living performed within the preceding 4 weeks. Scores range from 0 (independent) to 30 (dependent).

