9.3.1 Inclusion Criteria

Subjects must meet all of the following criteria to be included in this study:

1. Meets the core clinical research criteria of the NIA-AA for MCI due to AD ([Albert, et al., 2011](#)) or AD dementia ([McKhann, et al., 2011](#)) and is "staged" or classified as either MCI (Stage A and Stage B) or mild dementia (Stage B only) and also complies with the following:

Required at both Screening and Baseline:

- a. Subjective Memory Complaint with evidence of concern about a decline in cognition from the subject, informant, or clinician's observation
 - b. Cognitive impairment of at least 1 SD from age adjusted norms in delayed recall on the ISLT
 - c. FAQ ≤ 20
 - d. MMSE ≥ 20
2. Amyloid positive PET image based on centralized PET scan reading
 3. Male or female, age 50 to 85 years, inclusive at time of consent
 4. Must have an identified caregiver or informant who is willing and able to provide follow-up information on the subject throughout the course of the study. This person must, in the opinion of the investigator, spend sufficient time with the subject on a regular basis such that the caregiver or informant can reliably fulfill the study requirements and must provide separate written consent. The caregiver or informant need not be living in the same residence as the subject. If the caregiver or informant is not residing with the subject, the investigator has to be satisfied that the subject can contact the caregiver or informant readily during the times when the caregiver or informant is not with the subject. If in doubt about whether a subject's care arrangements are suitable for inclusion, the investigator should discuss this with the medical monitor. At visits where the CDR or FAQ are conducted, caregivers or informants need to either attend the visit in person along with the subject or be able to be contacted by telephone at the time of the visit. The investigator will determine whether attendance in person is required or whether telephone contact will be suitable and will base this determination upon the functional ability of the subject among other factors.

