Clinical Dementia Rating: Assesses 6 domains of subject function; memory, orientation, judgment and problem solving, community affairs, home and hobbies, and personal care.

CogState Brief Battery: A computer-based battery comprising 4 cognitive tests:

1. Detection – a simple reaction time test. Speed of response is the measure.
2. Identification – a simple choice reaction time test. Speed of response is the measure.
3. One Card Back – a simple working memory test. Accuracy of response is the measure.
4. One Card Learning – a visual learning and memory test. Accuracy of response is the measure.

International Shopping List Task: The ISLT is a verbal learning and memory test assessing both immediate and delayed recall.

Functional Assessment Questionnaire: The FAQ has 10 items concerned with performing daily tasks necessary for independent living. Either a caregiver or informant or the subject provides performance ratings on 10 complex activities of daily living performed within the preceding 4 weeks.

Volumetric Magnetic Resonance Imaging: vMRI will be used to evaluate disease modification, including the change from Baseline in terms of the measured hippocampal volume based upon the centralized measurement of the structure on repeated MRIs.

Pharmacokinetic Assessments

Blood and CSF samples will be collected for the determination of the concentrations of E2609. Analyses of metabolite concentrations may be performed depending on emerging data from other studies with E2609.

Pharmacodynamic, Pharmacogenomic and Other Biomarker Assessments

Brain atrophy will be measured by vMRI: see [Efficacy Assessments](#) (above).

The soluble biomarkers A β (1-x), A β (1-42), total tau (t-tau), and p-tau will be measured in CSF. BACE1 levels and activity in CSF will also be measured.

Amyloid PET imaging will be used to confirm that all subjects eligible for progression to the Baseline Period of the study have amyloid deposition in the brain. Longitudinal amyloid PET imaging will also be conducted after 18 months of treatment (or at ED, providing the subject has received at least 39 weeks of study drug). Longitudinal amyloid PET imaging will only be conducted through to the time at which acceptable 18-month PET scans have been obtained for at least 25 subjects per treatment arm for each amyloid PET ligand used.

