9.1.1.2 Baseline Period

All Screening Visit assessments must be completed (and eligibility to progress confirmed) before any Baseline Visit assessments are performed. The Baseline Visit assessments (per [Table 6](#) and [Section 9.5.1.2](#)) are to be completed as soon as possible after completion of the final Screening Visit assessment (ie, PET scan) such that all Screening Visit and Baseline Visit assessments are completed within 50 days.

Inclusion and exclusion criteria will again be reviewed, vital signs including weight will be recorded, and a 12-lead ECG will be conducted in triplicate. A routine physical examination will be conducted and a dermatological assessment and neurological examination will be performed. A urine pregnancy test will be conducted for females of childbearing potential. Blood will be collected from all subjects for clinical chemistry and hematology, lymphocyte subset analyses, Ig analyses, and PD assessments. Blood samples will be collected and stored for determination of a subject's previous exposure to infective pathogens in the event of AEs that warrant further investigation occurring at a later point in the study. Psychometric assessments will be administered to the subject in the order stated in [Table 6](#). The caregiver or informant needs to be present at this visit. The Columbia Suicide Severity Rating Scale (C-SSRS) will also be administered ([Section 9.5.1.5.11](#)).

CSF will be obtained at this visit for PK and PD assessments (see [Section 9.5.1.5.3](#)).

Blood will be collected from all subjects for pharmacogenomic (PGx) analyses of apolipoprotein E (*ApoE4*) and the *NAT2* phenotype of subjects enrolled in the study (see [Section 9.7.1.7.2](#)).

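### The FAQ respondent is not fixed: the memory-impaired subject may rate a scale that limits entry and serves as an endpoint, and the mode of informant contact for the CDR is neither held constant nor recorded

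*Protocol*

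**What the plan says.** **FAQ rater.** Section 9.5.1.3.1 states: "Either a caregiver or informant or the subject provides performance ratings (from 0 to 3". The ratings cover ten daily activities over the previous four weeks, for a total of 0 to 30. The synopsis gives the same open choice: "Either a caregiver or informant or the subject provides performance ratings on 10 complex activities of daily living". The file holds two versions of the protocol text, and section 9.5.1.3.1 reads the same on this in both. Neither version gives an order of preference or asks for the same rater at each visit.

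**Uses of the FAQ.** Section 9.3.1, criterion 1, sets FAQ ≤20 under the label "Required at both Screening and Baseline". Section 9.7.1.1.3 lists change in FAQ as an exploratory endpoint at 12 weeks and at 6, 9, 12, 15, 18, 19 and 21 months.

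**Informant.** Criterion 4 of section 9.3.1 requires an identified caregiver or informant for the whole study. For visits with the CDR or FAQ it adds that "caregivers or informants need to either attend the visit in person along with the subject or be able to be contacted by telephone".

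**Contact mode.** At those visits "the investigator will determine whether the caregiver or informant must attend in person or whether telephone contact will be suitable", and the investigator "will base this determination upon the functional ability of the subject among other factors" (section 9.5.1.3.1, repeated in criterion 4 and in Table 6 note d, with near-identical wording in Table 7 note p). For the Baseline Visit, section 9.1.1.2 says: "The caregiver or informant needs to be present at this visit". Section 9.1.1.1 says the same for Screening.

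**The concern.** Every subject must show delayed recall at least 1 SD below age norms (section 9.3.1, criterion 1b), yet may be asked to recall and rate four weeks of their own daily activities. The subject could rate at one visit and the informant at another. The difference between two raters would then enter the data as change in the subject. The same open choice applies at Screening and Baseline, where the score decides eligibility.

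The self-rating option also fills no gap, because the informant must in any case be present or reachable at each FAQ visit.

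The contact mode raises a related but lesser question. Function is part of what the CDR and FAQ measure, and function also guides the choice between in-person and telephone contact.

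These are rules of conduct and cannot be left to an analysis plan. The protocol requires neither the rater nor the mode to be recorded, and an unrecorded change cannot be examined later. The protocol is careful about consistency elsewhere. It fixes the time of day and order of testing, the PET agent within a subject, and the arm used for blood pressure.

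**Working it through.** **1. Does the open FAQ rater reach the primary endpoint?** Section 9.5.1.3.1 says: "The ADCOMS is derived from the ADAS-cog (4 items), the MMSE (2 items), and the CDR (all 6 items". The count is 4 + 2 + 6 = 12, which matches the total of 12 in section 9.2.4. The FAQ supplies 0 of 12, so the rater question stops at the FAQ entry limit and the FAQ endpoint.

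**2. Possible size for the FAQ endpoint.** The scale maximum is 10 × 3 = 30, as stated. The documents give no rater effect, switching rate or SD, so the following are assumptions:
- difference between raters d = 3 to 6 points
- proportion changing rater between Baseline and month 18, p = 0.2
- SD of FAQ change = 5, so variance = 25
- switching independent of true change

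Added variance = p(1 − p)d².
- d = 3: 0.2 × 0.8 × 9 = 1.44, and 1.44/25 = 5.8%
- d = 6: 0.2 × 0.8 × 36 = 5.76, and 5.76/25 = 23%

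If all switches ran in one direction, mean FAQ change would also shift by p × d, that is 0.6 to 1.2 points. If switching is equally common in all arms, this shift cancels between arms and the cost is noise.

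**3. What varies for the CDR.** The CDR supplies 6/12 = 50% of ADCOMS items by count. The share by weight cannot be computed, because the item weights are not given. Section 9.2.4 defines the CDR as an interview of both subject and informant, and criterion 4 asks for one identified informant throughout. The source is therefore fixed, and only the channel to the informant can vary.

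**4. Possible size for the CDR.** Between-arm bias = mode effect × difference in switching rates. With an assumed 0.5 box points and 10 percentage points, it is 0.5 × 0.10 = 0.05 on a 0 to 18 scale, and 0.05/18 ≈ 0.3% of the range. It cannot be converted to ADCOMS units without the weights.

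**5. Presence against telephone.** Sections 9.1.1.1 and 9.1.1.2 require the informant to be present at Screening and Baseline. A later paragraph of 9.1.1.1 allows telephone contact at Screening, and Table 6 note d, which governs both visits, allows it at CDR/FAQ visits. Sections 9.1.1.1 and 9.1.1.2 appear in only one of the two versions in the file. Table 6 note d allows telephone contact in both, so the conflict exists inside the version that requires presence.

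**The case against.** The FAQ sentence is a short description of an instrument, and the operational rules bring the informant to every FAQ visit. Where sections 9.1.1.1 and 9.1.1.2 apply, the informant is in the room at the two visits where FAQ ≤20 decides entry. Entry also depends on the NIA-AA criteria, MMSE ≥20, the ISLT criterion and the clinician's classification. This weighs against any claim that self-rating would let clearly dependent subjects through, and the documents do not support that claim. It does not settle who rates: an informant who is present or reachable is still only one of the permitted raters.

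A reader might infer that half of the ADCOMS lacks a constant source. The documents do not support this, because self-rating is offered for the FAQ only and the CDR always draws on subject and informant.

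A reader might also infer that a change of mode between Baseline and month 18 is built in. That rests on the presence wording in one version, which conflicts with that version's own telephone option. A change occurs only if an investigator later chooses the telephone, and a rule tied to function could equally keep worsening subjects in person.

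Finally, locking the Baseline mode could force in-person attendance for 18 months on informants who need not live with the subject. CDR data, and so ADCOMS data, could be lost as a result. That objection stands, and it limits what should be asked for.

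**Conclusion.** The point holds for the FAQ. The protocol expressly permits self-rating by memory-impaired subjects and sets no rule for keeping the rater constant, on a scale used both for entry and as an exploratory endpoint. The rise of 6% to 23% in the variance of FAQ change illustrates scale only. It depends on the assumed rater difference, switching rate and SD, and the documents contain no evidence on the size or direction of a rater effect. The primary endpoint is not affected by the choice of FAQ rater.

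For the CDR the point is secondary. The contact mode may vary between visits with the subject's function, while the source does not. The size of any mode effect is unknown and probably small, so recording the mode is proportionate and mandating it is not. The presence and telephone statements for Screening and Baseline contradict each other and need reconciling.

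**What to change.** - **FAQ rater.** In section 9.5.1.3.1 and the synopsis, strike the alternative that names the subject as a possible rater, and state that the identified caregiver or informant rates the FAQ at every visit.
- **Contact mode.** In criterion 4 of section 9.3.1, section 9.5.1.3.1, Table 6 note d and Table 7 note p, add that the mode (in person or telephone) and the informant are recorded at each CDR/FAQ visit. Both should be kept the same within a subject where feasible. In-person attendance should not become mandatory at later visits.
- **Reconciliation.** Align the presence requirement in sections 9.1.1.1 and 9.1.1.2 with the telephone option in 9.1.1.1 and Table 6 note d, so that one rule applies at Screening and one at Baseline.

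The cost is a few wording changes, two eCRF fields and slightly less flexibility for sites. Unavoidable changes of mode or informant remain possible, provided they are recorded.
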